Hematopoietic stem cell gene therapy (HSC-GT) using gamma retroviral vectors for the treatment of ADA-SCID has been under clinical investigation for more than 20 years (Cavazzana-Calvo et al., 2005, Engel et al., 2003). Clinical trials since the year 2000 have employed an approach that was first reported from two subjects treated in Milan, Italy and has recently been updated with 10 subjects (Aiuti et al., 2002, Aiuti et al., 2009). This approach involves discontinuing Adagen[®] (in subjects receiving Adagen as an ERT) and administering non-myeloablative conditioning prior to the infusion of ADA vector-transduced autologous CD34+ stem cells. In addition to the Milan study, variations on this protocol are currently under investigation in the UK, US, and Japan. More than 40 affected individuals (most of whom had been receiving Adagen) have been treated at these centers (Aiuti et al., 2002, Aiuti et al., 2009, Candotti et al., 2012, Cappelli and Aiuti 2010, Engel et al., 2007, Gaspar et al., 2006, Gaspar et al., 2013). Reconstitution of immune function is generally slow and may take 1 year or more. In most (but not all) affected individuals, stable ADA expression in lymphoid cells has been achieved, along with correction of metabolic abnormalities in erythrocytes, which has resulted in maintenance of good health without the need for ERT. In contrast to the experience with gene therapy for X-linked SCID, no subjects with ADA deficiency have thus far been reported to develop leukemia as a result of vector-associated insertional mutagenesis following gene therapy (Aiuti et al., 2007, Cappelli and Aiuti 2010). However, because of this concern and in order to achieve more effective ADA expression, the clinical investigation of gene therapy using lentiviral vectors is now underway (Farinelli et al., 2014).

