2. STUDY OBJECTIVES

2.1 **Objectives**

To conduct a registry study on patients, with adenosine deaminase severe combined immune deficiency (ADA-SCID) treated with Revcovi[®] and have periodic clinical and biochemical assessments for safety and dose adjustment based on adenosine deaminase (ADA) activity and erythrocyte deoxyadenosine nucleotide (dAXP) levels and/or clinical assessment by the treating physician. The study will include Adagen-naïve patients started on de novo enzyme replacement therapy (ERT) with Revcovi or converted from Adagen to Revcovi, over the course of 2 years and continued to be followed until the last enrolled patient has 2 years of follow up. Patients who are expected to receive 3 to 4 months of ERT prior to proceeding to hematopoietic stem cell transplantation (HSCT) or gene therapy will also be included in the study.

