For the STP-2270-002 subjects, the observational period for infections and hospitalizations after treatment initiation starts at the first dose of REVCOVI in the CLI-06814AA1-01 study. Infections and hospitalizations occurring during the STP-2279-002 study will not be included in the summary tables for the CLI-06814AA1-01 study.

The time periods will be defined as follows:

The year prior to treatment start with Revcovi will be defined as study day -365 to study day -1. For subjects younger than 1 year of age at the time of treatment initiation with Revcovi, it will be defined as the time period from the date of birth until study day -1 (time period calculated as date of first dose of Revcovi - date of birth + 1 day).

The end date of the time periods 1, 2, 3, 4, 5, 6, 7, 8, and 9 years after treatment initiation of Revcovi, respectively, will be defined as the earliest of the following events:

- End of time period (study day 365, 730, 1095, 1461, 1826, 2191, 2556, 2921, and 3286 respectively)
- Last date of treatment with Revcovi + 30 days
- Study completion date
- Study discontinuation date

- Date of death
- Date of transplantation

Infections occurring more than 30 days after the last dose of Revcovi will not be included in the calculation of the incidence rates, but will be included in the data listings and flagged.

The following analyses will be performed for the infections for each time period defined above:

- Number of events, number and percentages of affected subjects by SOC and PT. The denominator for the calculation of the percentages is the number of subjects with an observational period of 1 day or more in the respective analysis period, i.e. if the end date as defined above is not prior to the start date of the respective analysis period.
- Incidence rate of infections (in number of infections per year). The incidence rate will be based on the number of events, not on the number of affected subjects.
 95% CIs will be calculated for the incidence rates by the method of Ulm, assuming a Poisson distribution. The total observational period will be defined as the sum of the time periods for each subject from the start until the end date of the respective time period as defined above (end date start date + 1 day).

For both analyses, the infections will be slotted to the analysis periods based on the onset date of the adverse event.

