The number of hospitalizations will be analyzed similarly as the infections, i.e. number of hospitalizations, number and percentages of hospitalized subjects, incidence rates of hospitalizations for the time periods described above. The duration of hospitalizations will be described by descriptive statistics for continuous variables based on the number of hospitalizations. Subjects who are hospitalized in one analysis period and discharged from the hospital in the subsequent analysis period will be counted for the full hospitalization period (i.e. from admission to discharge) in the analysis period where they were hospitalized. All hospitalizations will also be presented in a data listing.

For subjects <18 years of age, height-for age and weight-for age and for patients between 24 months and 18 years of age, BMI-for age will be presented by z-scores at baseline and each intermediate collection time-point. Z-scores will be calculated programmatically based on reported age, gender, height and weight.¹ Z-scores and changes from baseline of z-scores to each visit (at which height and weight are assessed) will be summarized using descriptive statistics.

¹ http://www.cdc.gov/nccdphp/dnpao/growthcharts/resources/sas.htm

Overall survival will be analyzed by a Kaplan-Meier analysis. Kaplan-Meier survival curves will be plotted by subject status. Subjects who are alive at the end of the observational period will be counted as a censored observation. Observational period is the time from initiation of Revcovi until the date of study completion or study discontinuation (calculated as: date of study completion or study discontinuation – date of treatment initiation + 1 day) or from treatment initiation until the date of death, for subjects who die (calculated as date of death – date of treatment initiation + 1 day). Date of study completion or date of study discontinuation will be used as reported on the Patient Disposition page in the eCRF. For subjects transitioning from the STP-2279-002 study, overall survival will be calculated based on the date of the first dose of Revcovi in the STP-2279-002 study. If it is known that the subject died, but the date of death is unknown, it will be assumed that the subject died the day after their last assessment (whatever has been entered as last available date to the database, e.g. date of laboratory value, onset or resolution date of an AE, date of study discontinuation).

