8.2 Adverse Events and Other Complications

As part of this registry, only infections, clinically meaningful laboratory abnormalities (except infections) and Revcovi related adverse events will be recorded in the eCRF. A treatment-emergent AE will be defined as an AE with an onset date at or after the reported start date of Revcovi in the CLI-06814AA1-01 study and no later than 30 days after the last dose of Revcovi. All adverse events will be coded using the Medical Dictionary for Regulatory Activities (MedDRA) Version 22.1 or the most recent version prior to database lock. Summaries will be presented for all treatment-emergent adverse events (overall and by severity), adverse events determined by the investigator to be treatment-related (overall and by severity), serious adverse events (SAEs), adverse events causing discontinuation from Revcovi, and non-serious AEs. In addition to being summarized as adverse events, infectious complications and hospitalizations are considered efficacy measures as summarized in Section 7.2.3.

The frequency of adverse events will be summarized using descriptive statistics by system organ class (SOC), preferred term and subject status. Subjects are counted only once in each SOC category, and only once in each preferred term category. Treatment-related adverse event summaries will include adverse events with missing relationship to study drug. For the summaries by severity, subjects with multiple events are counted only once at the greatest non-missing severity. If all are of missing severity grade, then the AE term (SOC or PT) will be included in "Missing" severity category. Adverse events missing the flag indicating serious will be excluded from the summary of serious adverse events but included in the summary of non-serious adverse events. The total number of adverse events and serious adverse events and the corresponding yearly rates will also be reported.

Listings for all adverse events, deaths, serious adverse events and adverse events leading to study drug discontinuation will be presented. AEs from STP-2279-002 subjects with an onset date prior to the first documented dose of Revcovi in the CLI-06814AA1-01 study and a resolution date after the reported start date of Revcovi in the CLI-06814AA1-01 study or an outcome of ongoing, will be included in the AE listings but not in the summary tables.

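### SAP 7.2.3 does not say how planned HSCT/HSC-GT admissions are handled; as written they would normally enter the hospitalization rate, and their length of stay has no rule.

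*SAP*

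**What the plan says.** **Status of the endpoint.** SAP 8.2 states that "infectious complications and hospitalizations are considered efficacy measures as summarized in Section 7.2.3", and Protocol 13.2.3.5 says the same.

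**Who is in the population.** Both documents list subjects preparing for HSCT or HSC-GT as an enrolment class. SAP 2.1 describes them: "Patients who are expected to receive 3 to 4 months of ERT prior to proceeding to hematopoietic stem cell transplantation (HSCT) or gene therapy".

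**The window.** SAP 7.2.3 ends the periods for years 1 to 9 at the earliest of six dates. These are the end of the period, "Last date of treatment with Revcovi + 30 days", study completion, study discontinuation, death and "Date of transplantation". The any-time period, last in the list of analysis periods, has no end date of its own.

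**Counting.** Hospitalizations follow the method for infections, which are placed in a period by onset date, so the natural counterpart is the admission date. Rates are events divided by summed observation time.

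**Duration.** Length of stay is summarized per hospitalization. The only rule concerns subjects admitted in one analysis period and discharged in the subsequent one, who "will be counted for the full hospitalization period (i.e. from admission to discharge) in the analysis period where they were hospitalized".

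**The concern.** For a subject who is being bridged, the admission for the transplant is the planned next step. It says little about how well Revcovi controls the disease. The window closes at transplantation rather than at admission, so such an admission is normally still inside it. It then sits in the same count and rate as admissions for infection or other illness.

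Bridged subjects contribute little observation time, so one certain event each can weigh heavily in a pooled rate. A long transplant stay can also dominate a mean length of stay that rests on few admissions.

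The comparison with the year before Revcovi is exposed as well. Subjects who start Revcovi after not responding to HSCT or HSC-GT are eligible and may carry a transplant admission in that earlier year. The distortion can therefore run in either direction.

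**Working it through.** The plan gives no sample size, expected hospitalization rate or number of bridged subjects, so there is no figure of its own to reproduce. I applied the written rule and then illustrated its size on stated assumptions.

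**1. Is the admission inside the window?** Let A be the admission day, D the transplantation day, L the last Revcovi dose and E the earliest other stop date. The admission counts if A ≤ min(D, L + 30, E). I take transplantation to include HSC-GT, because the SAP schedule tables head the Month 1 and Month 6 columns with both procedures and SAP 13.3 calls those visits post-transplantation. With L = 100 and E = 365:

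| A | D | Window end | Counted |
|---|---|---|---|
| 100 | 100 | 100 | yes |
| 100 | 107 | 107 | yes |
| 110 | 117 | 117 | yes |
| 120 | 130 | 130 | yes |
| 130 | 137 | 130 | yes |
| 131 | 138 | 130 | no |

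An inpatient transplant admission cannot start after the transplantation date. It is counted unless Revcovi stopped more than 30 days before admission or another stop date came first. Protocol 5.1 supports admission before infusion for gene therapy, since that approach involves "administering non-myeloablative conditioning prior to the infusion of ADA vector-transduced autologous CD34+ stem cells". It does not say that conditioning is inpatient.

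**2. Is there a filter elsewhere?** I found none. Protocol 14.7.1 has hospitalizations entered in the EDC system without separating planned from unplanned. Protocol 10.8.2 limits pharmacovigilance reporting to causally related hospitalizations, but it does not limit what the efficacy summary counts.

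**3. Weight in one subject.** With 3 to 4 months of ERT, one admission is 1/(3/12) = 4.0 to 1/(4/12) = 3.0 per person-year (PY). The SAP pools events over total time, so this shows leverage and is not a reported quantity.

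**4. Pooled year-1 rate.** Assumptions: 20 subjects; k bridged at 3.5 months with one planned admission each; the others followed 12 months; background b admissions per PY, with events rounded. PY = k × 3.5/12 + (20 − k). Entries are the rate per PY without → with the planned admissions.

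| k | PY | b = 0.2 | b = 0.5 | b = 1.0 | Added (k/PY) |
|---|---|---|---|---|---|
| 2 | 18.58 | 0.22 → 0.32 | 0.48 → 0.59 | 1.02 → 1.13 | 0.11 |
| 5 | 16.46 | 0.18 → 0.49 | 0.49 → 0.79 | 0.97 → 1.28 | 0.30 |
| 10 | 12.92 | 0.23 → 1.01 | 0.46 → 1.24 | 1.01 → 1.78 | 0.77 |

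For k = 5 and b = 0.5 the rates are 8/16.46 = 0.49 (95% CI 0.21 to 0.96) and 13/16.46 = 0.79 (0.42 to 1.35). The limits are exact Poisson, standing in for the SAP's Ulm interval.

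**5. Length of stay.** Assume 8 other stays of 5 days and 5 transplant stays of s days. The mean with whole stays is (8 × 5 + 5 × s)/13, which gives 8.5, 13.8 and 19.2 days for s = 14, 28 and 42. Without the transplant stays it is 5. If each were counted only for an assumed 7 days before transplantation, it would be (40 + 35)/13 = 5.8. The SAP does not say which applies. Observation time stops at transplantation in any case, so bed-days and person-time would not match if whole stays are used.

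**6. The any-time period.** The end-date list names only years 1 to 9. A separate sentence keeps infections later than 30 days after the last dose out of the rates, and it carries over to hospitalizations by analogy. The transplantation stop and the end of person-time are not stated for this period.

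**The case against.** **Inclusion is conditional.** It needs an inpatient admission before any stop date. Protocol 7.4 and 11.3 run follow-up until HSCT or HSC-GT, so a completion date might be recorded at or before admission. Against that, transplanted subjects are followed to six months after the last dose. Neither document says which date is entered, and the hospitalization eCRF page is not shown. The condition stands and is part of the point.

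**The full-stay sentence is narrow.** A reader might infer from it that the SAP orders the whole transplant stay to be counted. It does not: the sentence covers stays that cross into the next analysis period. Full duration is only the probable programming in the absence of another rule.

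**Nothing is scored as a failure.** A reader might infer that a transplant admission becomes an efficacy failure of Revcovi. The documents define no failure or responder endpoint for hospitalization, and Protocol 13.2.1 rules out hypothesis tests. The event enters a descriptive rate and a length-of-stay summary.

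**The affected group is not known.** Placing the effect in the Adagen-naïve group is an assumption, because subject status comes from the eCRF and bridging is not tied to it. For subjects bridged over 3 to 4 months, only the year-1 and any-time periods are affected.

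**Adverse events.** SAP 8.2 counts events as treatment-emergent if they start "no later than 30 days after the last dose of Revcovi", with no stop at transplant. A reader might call that inconsistent with the infection rates. But Protocol 13.2.3.5 sets that same 30-day window, and a safety window may differ from an efficacy window. Splitting adverse events at conditioning is a preference, and I do not ask for it.

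**Listings and endpoint definition.** Transplants are counted in disposition, and hospitalizations and procedures are listed, so a careful reader could trace these stays. The summary rate would still mix them. The endpoint in Protocol 6.3 also excludes no planned admissions. That argues for reporting both ways rather than removing them.

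**Conclusion.** The point holds as a gap in SAP 7.2.3. Read as written, a planned inpatient HSCT/HSC-GT admission normally enters a rate that both documents call an efficacy measure, subject to the conditions in step 1 of the check. The handling of a stay that crosses transplantation is unspecified, and the any-time period lacks an end date.

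The size cannot be fixed from the documents. On the assumptions above, the added rate runs from 0.11 per PY (2 of 20 bridged) to 0.77 per PY (10 of 20). It matters most when the background rate is low. These figures are illustrations and not predictions. They support no claim of a fixed direction of bias in the before/after comparison, because transplant admissions can fall on either side of the Revcovi start.

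**What to change.** In SAP 7.2.3:

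- Flag every admission whose reason is HSCT or HSC-GT, including cell collection and conditioning.
- Report hospitalization count, rate and duration with and without the flagged admissions, and tabulate the flagged ones separately.
- Apply the same flag to transplant admissions in the year before Revcovi.
- Give the any-time period the same end-date rule as the yearly periods.

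There is no need to cut every stay at the end of observation. That would also shorten stays unrelated to transplant.

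The cost is SAP wording and one extra table. The reason for admission must be reviewed for the transplanted subjects, whom SAP 6.2 already counts. The endpoint itself and clinical conduct do not change.

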9.5 Withdrawal of Enrolled Subjects

In the absence of a significant protocol violation, every effort will be made by the Investigator to keep subjects in the study. The primary reason for a subject withdrawing prematurely should be selected from the following standard categories:

- AE clinical or laboratory events that in the judgment of the Investigator require discontinuation of Revcovi in the best interests of subject.
- Death death of the subject, whether study related or not.
- Withdrawal of Consent subject desires to withdraw from further participation in the study in the absence of a medical need to withdraw determined by the Investigator.
- Lost to follow-up the subject did not return for one or more follow-up visit(s) following the start of Revcovi treatment.
- Subject meets withdrawal criteria the subject's condition meets the criteria for withdrawal from the study (Section 9.5.1).
- Other causes of premature termination from the study other than the above (e.g., termination of study by Chiesi Farmaceutici S.p.A., subject relocated).

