11.2 Revcovi Treatment Period

The assessments and schedule described in the following subsections are suggested based on recommendations described in the Revcovi PI.

Monitoring for trough plasma ADA activity and trough erythrocyte dAXP levels is essential to establish therapeutic levels of Revcovi and to maintain detoxification. The schedule of monitoring listed in the PI and in this protocol are recommended and not required. Clinicians should individualize the schedule of monitoring to assess the effect of Revcovi on trough plasma activity of ADA, erythrocyte dAXP, and immune function (lymphocyte counts, lymphocyte subsets and immune response) while balancing the risk of phlebotomy and subject visit burden. The listing for the schedule of assessments (Appendix 1 and Appendix 2) provides a template for reporting of monitoring and is not a rigid requirement.

Safety laboratory assessments should be collected, if available, but these assessments are not required (Section 10.5.3). Immunogenicity testing should also be performed, if indicated, in accordance with the Revcovi PI (see Section 10.5.4).

With the exception of ADA and dAXP assessments, a microtainer should be used for blood collection for subjects younger than 10 years of age whenever possible.

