11.2.1 Adagen-transitioning subjects

Visit frequency is determined by Provider/Subject as needed for clinical standard of care with recommendations in the Prescribing information.

11.2.1.1 Treatment Week 4

At Treatment Week 4 (\pm 1 week), the subject should return to the study site and have the following procedures performed as per suggested schedule of assessments:

- AE assessment
- Concomitant medications
- Revcovi dosing and compliance
- Assessment of infectious complications and hospitalizations
- Assessment of concomitant use of ADA inhibitors and Ig replacement therapy and any procedures performed since last study visit
- Vital signs
- Physical examination (including height and weight)
- Safety Laboratory assessments (if available)
- Immunogenicity

Blood samples should be obtained prior to administration of Revcovi for:

• Trough plasma ADA activity

11.2.1.2 Treatment Week 8

At Treatment Week 8 (\pm 1 week), the subject should return to the study site and have the following procedures performed as per suggested schedule of assessments:

- AE assessment
- Concomitant medications
- Revcovi dosing and compliance
- Assessment of infectious complications and hospitalizations
- Assessment of concomitant use of ADA inhibitors and Ig replacement therapy and any procedures performed since last study visit
- Vital signs
- Physical examination (including height and weight)
- Safety Laboratory assessments (if available)
- Immunogenicity

Blood samples should be obtained prior to administration of Revcovi for:

• Trough erythrocyte dAXP

Trough plasma ADA activity

11.2.1.3 Treatment Week 12

At Treatment Week 12 (± 1 week), the subject should return to the study site and have the following procedures performed as per suggested schedule of assessments, if needed:

- AE assessment
- Concomitant medications
- Revcovi dosing and compliance
- Assessment of infectious complications and hospitalizations
- Assessment of concomitant use of ADA inhibitors and Ig replacement therapy and any procedures performed since last study visit
- Vital signs
- Physical examination (including height and weight)
- Safety Laboratory assessments (if available)
- Immunogenicity

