6.5 Medical History

Medical history at screening will be listed, but not summarized.

6.6 **Prior ADA-SCID Treatment excluding ERT**

The number and percentages of patients who received prior ADA-SCID treatment (excluding ERT) will be summarized by type of treatment and overall. Free text for other treatments will be listed but not summarized.

6.7 **Prior ERT Treatments**

Prior ERT medications (Adagen treatment) will be summarized for all subjects transitioning from Adagen to Revcovi and for the STP 2279-002 subjects. The following parameters will be summarized: duration of Adagen treatment (i.e. last dose – first dose +1 day), units per administration, administration frequency, total weekly dose (as reported on the eCRF) and calculated total weekly dose per kg body weight for the prescribed and actual dose. For subjects who were treated according to the prescription, actual dose will be derived from the prescribed dose. The number and percentages of subjects who stopped Adagen treatment prior to the first dose will also be reported together with summary statistics for the time from the last dose of Adagen until the first dose of Revcovi. For the STP 2279-002 subjects, the duration of treatment with Revcovi in the STP 2279-002 study (last dose – first dose of Revcovi in the STP 2279-002 study + 1 day) will be summarized. All prior treatments with Adagen will also be presented in a data listing.

6.8 **Physical Examination**

Physical examination results at screening will be reported as medical history and will be analyzed and presented as such.

6.9 **Protocol Deviations**

A full list of protocol deviations will be presented in the clinical study report. Because this is a registry with no scheduled assessments or planned treatments, on-study protocol violations are restricted to administrative and operational deviations (e.g. delayed reporting of an SAE or transmission of clear names together with SAE reports). Protocol deviations will be listed but not summarized.

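### SAP 7.2.3 sets no last-known-alive limit, so survival can be overstated and event rates understated for lost subjects: modestly, and only if the disposition date falls after last contact

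*SAP*

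**What the plan says.** **Overall survival (SAP 7.2.3).** The analysis is Kaplan-Meier, plotted by subject status. The SAP states: "Subjects who are alive at the end of the observational period will be counted as a censored observation". The observational period runs from the start of Revcovi to completion, discontinuation or death, and for the first two: "Date of study completion or date of study discontinuation will be used as reported on the Patient Disposition page in the eCRF". Subjects whose vital status is unknown have no rule of their own.

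**Infections and hospitalizations (SAP 7.2.3).** Time at risk in each analysis period ends at the earliest of several dates. One is "Study discontinuation date". Another is the last Revcovi treatment plus 30 days. The remainder are the end of the period, study completion, death and transplantation.

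**Deaths of unknown date (SAP 7.2.3).** The subject is taken to have died one day after the last date available in the database. The examples given for that last date include the study discontinuation date.

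**Treatment duration (SAP 8.7).** For subjects still on Revcovi at the end of observation, duration is counted to the date on the disposition page.

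**Adverse events (SAP 8.2).** Yearly rates are promised, but their denominator is not defined.

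**The concern.** A subject contributes information on survival or infection only while someone can observe an event. Once contact is lost, a death or infection will probably not reach the database. If the disposition page carries a date well after the last contact, the time between the two adds to the risk set and to the rate denominator but cannot add to the event count. Any error therefore runs one way: survival up, event rates down.

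The design leaves room for such gaps. Protocol 7.1 follows subjects until the last one enrolled reaches 24 months, and SAP 7.2.3 sets analysis periods out to year 9. Survival and infection rates are also among the main clinical outputs of what Protocol 5.4 describes as a post-marketing commitment.

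**Working it through.** The plan states no sample size, loss rate or expected event count, so it has no figure to reproduce. Every input below is an assumption chosen to show a range. L is the lag in months from last contact to the disposition date.

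**1. Person-time and rates.** Assume lost subjects are truly observed for a mean of 15 months and the others for 36, and let f be the share lost. True mean person-time is 36(1 − f) + 15f. With the lag it is 36(1 − f) + (15 + L)f. The event count is unchanged, so the rate is multiplied by the first divided by the second.

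- f = 5%, L = 3: 34.95 / 35.10 = 0.996, so the rate is 0.4% lower.
- f = 20%, L = 12: 31.80 / 34.20 = 0.930, so the rate is 7.0% lower.

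Fall in event rate:

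| Share lost | L = 3 | L = 6 | L = 12 |
|---|---|---|---|
| 5% | 0.4% | 0.9% | 1.7% |
| 10% | 0.9% | 1.7% | 3.4% |
| 20% | 1.9% | 3.6% | 7.0% |

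**2. One Kaplan-Meier step.** With n subjects truly at risk and k who are out of contact but still counted, one death gives a factor of 1 − 1/(n + k).

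- n = 10: 0.900 with k = 0, and 0.929 with k = 4.
- n = 20: 0.950 with k = 0, and 0.958 with k = 4.

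Because the curves are drawn by subject status, risk sets may be small, and small sets are the more sensitive.

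**3. Survival at 24 months, by simulation.** Assume 30 subjects, 5% annual mortality (true 24-month survival 0.95² = 0.9025), follow-up to 36 months, exponential loss with the stated share lost by 24 months, and deaths after loss unseen. There were 4,000 runs per setting. The table gives the excess, in percentage points, from censoring at last contact plus L instead of at last contact.

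| Lost by 24 months | L = 3 | L = 6 | L = 12 |
|---|---|---|---|
| 10% | 0.12 | 0.22 | 0.37 |
| 20% | 0.24 | 0.45 | 0.77 |
| 40% | 0.55 | 1.00 | 1.64 |

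Censoring at last contact gave 0.901 to 0.903 in every setting, close to the true value.

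**4. No lag.** With L = 0 the two rules coincide and every difference is zero.

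**5. Does the 30-day limit protect the rates?** It does if a true last dose is recorded. That may be hard to establish for a lost subject: drug comes from a specialty pharmacy (Protocol 8.2), there is no drug accountability (Protocol 8.6), and exposure is summarized from prescribing data while diaries are only listed (SAP 8.7). SAP 8.7 carries treatment to the disposition date for treatment duration. SAP 7.2.3 does not say whether the same convention sets the last treatment date for the limit. If it does, the limit gives no protection. In either case it does not apply to overall survival.

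**The case against.** The strongest reply is that the premise is conditional. A reader might infer that the disposition date is the day the site closed the record, so that event-free time is certainly added. The documents do not say so. They say only that the reported date is used, and a site may well enter the last contact. This stands, and it is why the point is worded as a possibility.

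There are safeguards. The protocol synopsis provides for visits and/or phone calls to confirm survival status, Protocol 9.5.2 seeks a complete final evaluation at withdrawal, and the 30-day limit may shorten infection and hospitalization time. These reduce the problem. They do not supply a rule for a subject who cannot be reached.

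A reader might also infer that the SAP already derives a last-contact date for undated deaths and merely omits it for losses. That goes too far: the undated-death rule can itself return the discontinuation date.

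Finally, Protocol 9.5 describes lost to follow-up thus: "the subject did not return for one or more follow-up visit(s) following the start of Revcovi treatment". Visits are flexible ("Visit frequency is determined by Provider/Subject as needed for clinical standard of care with recommendations in the Prescribing information") and the schedule "provides a template for reporting of monitoring and is not a rigid requirement", so a reader might infer that one missed visit makes a subject lost and that losses are misclassified. The lead-in to the list rules this out: "The primary reason for a subject withdrawing prematurely should be selected from the following standard categories". The wording codes a reason for subjects already leaving. It does not remove anyone, and the chance of missing at least one suggested visit estimates neither losses nor misclassification.

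**Conclusion.** The point holds in conditional form. SAP 7.2.3 counts every subject not known dead as alive up to the disposition date, and lets infection and hospitalization time run to the discontinuation date, with no last-known-alive limit. Where that date is later than last contact for a lost subject, survival can be overstated and rates understated.

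The effect is modest under the assumptions above: rates 0.4% to 7.0% lower for 5% to 20% lost, and 24-month survival 0.1 to 1.6 points higher for 10% to 40% lost, with lags of 3 to 12 months. Larger figures need longer lags or heavier early loss. For example, 17 subjects followed for 24 months and 3 lost at month 8 give 17 × 24 + 3 × 8 = 432 months. A 24-month lag adds 72 months and lowers rates by 72/504 = 14.3%, but nothing in the documents points to such a lag. A 3-month lag in the same example adds 9 months and lowers rates by 9/441 = 2.0%.

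All analyses are descriptive, so no test or error rate is affected. The lost-to-follow-up wording in Protocol 9.5 is at most a matter for clarification, not an error.

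**What to change.** In SAP 7.2.3, and for the yearly rates in SAP 8.2:

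- For subjects discontinued as lost, or without a final contact, end overall survival and the infection, hospitalization and AE person-time at the earlier of the disposition date and the last documented contact or assessment.
- Exclude the disposition date itself when deriving that last contact. The undated-death rule cannot be reused unchanged, because it admits the discontinuation date.
- State that the last-dose-plus-30-days limit uses the last documented dose, not the carry-forward to the disposition date in SAP 8.7.

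Optionally, Protocol 9.5 could ask sites to record contact attempts before selecting the lost category.

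The cost is a few lines of SAP text and one derived date. The downside is slightly less person-time. If no subject has a lag, the results do not change.
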